Subjects will be administered study medication according to the dose titration schedule in [Section 7.2.1](#).

Subjects will be allowed to back-titrate 1 dose level during the Titration Period. Subjects are to complete the Titration Period at the back-titrated dose level and remain at this dose level for the duration of the Maintenance Period. If AEs occur during the Titration Period that are thought to

be the result of excessive dopaminergic stimulation (eg, intolerable nausea/vomiting), subjects should be back-titrated to their previous dose level and commence the Maintenance Period immediately. Subjects who do not tolerate the assigned dose in the first week (placebo or 1mg/24h) will be withdrawn from the study. If subjects withdraw due to lack of efficacy, they are eligible to roll over to the open-label study, RL0007, after the 3 weeks of the Titration Period are completed.

The Titration Period will be followed by a 12-week Maintenance Period. Subjects will remain at the assigned (or back-titrated) dose level throughout the Maintenance Period. At the end of the Maintenance Period, subjects will enter a Taper Period lasting up to a maximum of 4 days (de-escalation of study medication), followed by a 30-day Safety Follow-Up Period.

Visits will be scheduled every week during the Titration Period. During the Maintenance Period, visits will be scheduled every 4 weeks. There is a 4-day interval until the end of the Taper Period, followed by a 30-day interval (± 5 days) until the Safety Follow-Up Visit. Details are provided in the schedule of study assessments in [Section 5.2](#).

Plasma concentration of unconjugated rotigotine will be summarized by dose levels and visit. Plasma samples will be collected at Visit 6 and Visit 9.

An interim analysis for futility (for the primary outcome measures only), with the possibility of stopping the study early, stopping a dose arm, or continuing the study as planned, will be performed with approximately 33% of the planned number of evaluable subjects; recruitment will not be stopped for the interim analysis. The futility criteria are defined in [Section 13.7](#).

An overview of the study activities is given in [Table 5-1](#) and [Figure 5-1](#).

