	Day -28 to Day -1	Day 0	Day 1	Day 8	Day 15	Day 22	Day 50	Day 78	Day 106	Day 110		
Assessment												

BL=Baseline; BMI=body mass index; CGI=Clinical Global Impressions; C-SSRS=Columbia-Suicide Severity Rating Scale; ECG=electrocardiogram; eCRF=electronic Case Report form; EOT=End of Titration; hCG=human chorionic gonadotropin; IRLS=International Restless Legs Scale; IRT=interactive response technology; mMIDI=Modified Minnesota Impulsive Disorder Interview; PK=pharmacokinetic; Rand=randomization; RLS=Restless Legs Syndrome; SOM=Start of Maintenance; V=Visit; WD=withdrawal

Note: The date of informed consent may be prior to screening assessments and study procedures.

Note: Rescreening is allowed with the permission of the Study Physician or representative.

Note: For Visit 2, there is a visit window of +3 days to allow for direct-to-subject shipment of study medication. Visit 3/Day 1 is the first day of study medication exposure. All subsequent visits are calculated based on Visit 3/Day 1.

Note: Visit 6 is the end of the Titration Period and start of the Maintenance Period. Visit 9 is the end of the Maintenance Period and start of the Taper Period.

Note: All visits are via telemedicine calls, with the exception of Visit 1, Visit 6, Visit 9, and SFU. Unscheduled visits are at the discretion of the investigator and may be telemedicine calls.

^a The visit window for Titration Visits is ±1 day per visit relative to Visit 3 (day of first dose). The visit window for visits during the Maintenance Period, including the End of Maintenance Visit, is ±2 days per visit. The Taper Period, which will last up to a maximum of 4 days, will start on the day after the End of Maintenance Visit. The visit window for Safety Follow-Up Period is 30 days±5 days relative to the end of the Taper Period. Following dose de-escalation, subjects may be eligible to participate in the open-label, long-term follow-up study (RL0007) at any time prior to the Safety Follow-Up Visit (see Section 5). The Safety Follow-Up Visit is for subjects not entering RL0007.

^b Assessments to be performed are at the investigator's discretion.

^c C-SSRS is required if the Un-scheduled Visit is conducted due to safety or efficacy reasons.

^d Pregnancy test and menstrual function for all female subjects; serum pregnancy test at Screening and urine pregnancy test at all other visits. A positive urine pregnancy test must be confirmed by a serum pregnancy test.

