8.5 Safety Follow-Up Visit (if applicable)

The visit window for Safety Follow-Up Period is 30 days \pm 5 days relative to the end of the Taper Period. Following dose de-escalation, subjects may be eligible to participate in the open-label, long-term follow-up study (RL0007) at any time prior to the Safety Follow-Up Visit (see [Section 5](#)). The Safety Follow-Up Visit is for subjects not entering RL0007.

Information listed below will be collected by the investigator and/or study staff, as appropriate, via a telephone or telemedicine call with the subject/legal representative.

- Menstrual function for all female subjects

The assessments listed below will be completed by mobile study personnel at the subject's/legal representative's home and records of the procedures will be obtained, with information noted as part of the subject's study record.

- Brief physical examination, including body weight, height, BMI, and vital signs
- Neurological examination
- 12-lead ECG

For lab collections and procedures listed below, mobile study personnel will be sent to the subject's/legal representative's home. Samples will be prepared and sent to a central laboratory for processing and analysis, and results will be provided to the study site.

- Safety laboratory tests
- Urine pregnancy test for all female subjects
- Hormone status

Assessments listed below will be completed either by the subject or investigator/trained study staff, as required. Assessments that require interviews will be completed via a telephone or telemedicine call.

- C-SSRS (Since Last Visit version)

Additional assessments and procedures are listed below.

- Recording of medication and procedures. See [Section 8.2.1](#).
- AE assessment. See [Section 8.2.1](#).
- Contact IRT. The IRT is contacted to process the subject's completion of the study.
- Return unused study medication. See [Section 8.3.1](#).

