11.1.2.3 Additional procedures for reporting serious adverse events

If an SAE is reported, UCB must be informed within 24 hours of receipt of this information by the site (see contact information for SAE reporting listed in the Serious Adverse Event Reporting section at the front of the protocol). The investigator must forward to UCB (or its representative) a duly completed “Investigator SAE Report Form for Development Drug” (SAE Report form) provided by UCB, even if the data are incomplete, or if it is obvious that more data will be needed in order to draw any conclusions. Information recorded on this form will be entered into the global safety database.

An Investigator SAE Report form will be provided to the investigator. The Investigator SAE Report form must be completed in English.

It is important for the investigator, when completing the SAE Report form, to include the assessment as to a causal relationship between the SAE and the IMP administration. This insight from the investigator is very important for UCB to consider in assessing the safety of the IMP and in determining whether the SAE requires reporting to the regulatory authorities in an expedited manner.

Additional information (eg, autopsy or laboratory reports) received by the investigator must be provided within 24 hours. All documents in the local language must be accompanied by a translation in English, or the relevant information included in the same document must be summarized in the Investigator SAE Report form.

The investigator is specifically requested to collect and report to UCB (or its representative) any SAEs (even if the investigator is certain that they are in no way associated with the IMP), up to 30 days from the end of the study for each subject, and to also inform participating subjects of the need to inform the investigator of any SAE within this period. Serious AEs that the investigator thinks may be associated with the IMP must be reported to UCB regardless of the time between the event and the end of the study.

Upon receipt of the SAE Report form, UCB will perform an assessment of expectedness of the reported SAE. The assessment of the expectedness of the SAE is based on the Investigator's Brochure.

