3.2.1.2 Date of last patch removal

The date of last patch application is documented on the Study Termination page of the eCRF. If the date of last patch application on this page is missing the last available kit start date on the Drug Accountability log form will be used as the date of last patch application. Thus, the date of the last patch removal is defined as the date of the last patch application + 1.

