3.2.2 Study periods

The following time periods are defined for this study.

- Screening Period:

The Screening Period starts with Visit 1 and ends the day before the date of the first patch application. This period includes Visit 2/Day 0 at which the subjects are randomized, and study medication is assigned and shipped.

- Titration Period:

The Titration Period starts at the day of the first patch application (Day 1) and ends on the day prior to Visit 6. In case of a premature withdrawal before Visit 6, the Titration Period ends at the day of the Withdrawal Visit. If the Withdrawal Visit is missing or the date of the last patch removal (or last known patch removal) is before the Withdrawal Visit, the Titration Period ends at the day of last patch removal.

- Maintenance Period:

The Maintenance Period starts at Visit 6 and ends at Visit 9. If the subject withdraws prior to Visit 9, the Maintenance Period ends at the day of the Withdrawal Visit date or the last patch removal date (or last known patch removal date), whichever is earlier.

- Taper Period:

The Taper Period starts at the date of last maintenance patch removal and ends at the day of last patch removal. If the day of last patch removal is on the date of last maintenance patch removal, i.e., no de-escalation was performed for any reason, then no Taper Period is defined for this subject.

- Treatment Period:

The Treatment Period comprises the Titration Period, the Maintenance Period, and the Taper Period, i.e., it starts with the day of first patch application and ends on the maximum end date of the Titration, Maintenance and Taper periods.

- Safety Follow-Up Period:

The Safety Follow-Up Period starts the day after the end of the Treatment Period and ends at the date of the Safety Follow-Up Visit. However, AEs starting within 30 days following the date of last patch removal will be considered for analysis, even if the start date is after the

date of last study assessment. If the subject rolls over into the RL0007 study, then the Safety Follow-up Period dates will be missing.

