10.2 Adverse events

Adverse events will be documented throughout the entire study on an ongoing basis. TEAEs are defined as events that started during the Treatment Period or within 30 days following the end of the Treatment Period (i.e., on or after the date of first patch application and within 30 days following the date of last patch removal) or any unresolved event already present before administration of treatment that worsens in intensity following exposure to the treatment. For AEs with a partial or missing start date, the imputation rules as described in [Section 4.2.2](#) will be applied.

Adverse events with a missing start date are defined as treatment-emergent if the end date of the AE is not on or before the date of first patch application.

An AE with action taken regarding study medication reported on the AE page of the eCRF as “drug permanently withdrawn” will be regarded as an AE leading to discontinuation of study medication.

Adverse events which have the question “Serious Adverse Event?” answered “yes” or missing are considered serious.

Treatment emergent AEs will be tabulated by MedDRA SOC, High Level Term (HLT) and PT. The number and percentage of subjects experiencing each event at least once will be summarized in addition to the number of events. In summaries of TEAEs by relationship and intensity, respectively, the number of events will not be presented.

All summaries will be sorted alphabetically by SOC and HLT and by frequency of events (PT) in the total rotigotine group within HLTs. If there is more than one PT with the same frequency in the total rotigotine group these events will be sorted alphabetically.

An overview of the incidence and frequency of all TEAEs, serious TEAEs, TEAEs leading to discontinuation of study medication, related TEAEs, severe TEAEs, all deaths and TEAEs leading to death will also be provided.

The following tabular summaries will be presented also.

- TEAEs
- TEAEs by intensity
- TEAEs by maximum intensity
- TEAEs by relationship to study medication per the Investigator
- Serious TEAEs
- Serious TEAEs by Relationship to study medication per the Investigator
- non-serious TEAEs above reporting frequency threshold of 5%

Individual subject data listings will be presented for all AEs.

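### The TEAE window does not stop at entry to the open-label study RL0007, so any later event recorded in SP1006 would be counted under the randomised arm, placebo included

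*SAP*

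**What the plan says.** **TEAE window.** SAP 10.2 takes as treatment-emergent any event starting "on or after the date of first patch application and within 30 days following the date of last patch removal", plus pre-existing events that worsen after exposure. SAP 3.2.1.2 fixes the anchor: "the date of the last patch removal is defined as the date of the last patch application + 1".

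**Reach of the window.** SAP 3.2.2 adds that "AEs starting within 30 days following the date of last patch removal will be considered for analysis, even if the start date is after" the last study assessment.

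**Rollover subjects.** The only special handling is in the same part of SAP 3.2.2: "If the subject rolls over into the RL0007 study, then the Safety Follow-up Period dates will be missing".

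**When RL0007 can start.** Protocol 8.5 says that after dose de-escalation "subjects may be eligible to participate in the open-label, long-term follow-up study (RL0007) at any time prior to the Safety Follow-Up Visit". For subjects who withdraw for lack of efficacy, Protocol 5.1 says that "they are eligible to roll over to the open-label study, RL0007, after the 3 weeks of the Titration Period are completed".

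**Collection after rollover.** The notes to the schedule in Protocol 5.2 state: "The Safety Follow-Up Visit is for subjects not entering RL0007". For serious events, Protocol 11.1.2.3 asks the investigator to collect and report "up to 30 days from the end of the study for each subject", with no exception for rollover.

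**Arm used.** SAP 3.1 and 3.6 summarise by randomised treatment, whatever dose was received.

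**The concern.** The 30 days after last patch removal are meant to catch late effects of the randomised treatment. For a subject who enters RL0007, part or nearly all of those days can be time on a different, open-label treatment. If that treatment is rotigotine, a placebo subject's first exposure to active drug falls inside the window that defines placebo TEAEs. A subject from an active arm would have events from a second exposure added to the first.

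This matters because occurrence of TEAEs is one of the two primary safety variables in Protocol 4.2.1, and the TEAE tables by arm survive the early termination. The inferential efficacy analysis, the per-protocol analysis and the interim analysis do not. SAP Amendment 2 revised both 3.2.2 and 10.2 and left this boundary undefined.

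**Working it through.** The documents give no figure for this rule, so there is nothing to reproduce. The check is whether RL0007 time can fall inside the window, and for how many days.

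**1. Do the blank Safety Follow-Up dates cut the window?** No. The TEAE rule runs from first patch application to last patch removal plus 30 days. It does not use the Safety Follow-Up Period dates, so setting them to missing changes nothing.

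**2. Window length.**
- Removal day = last application day + 1 (SAP 3.2.1.2).
- Window end = removal day + 30 (SAP 10.2).
- Open-label days in the window = 30 − gap, where the gap is the number of full days between the removal day and the first RL0007 dose. An open-label patch applied on the removal day itself would add one day.

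The gap is an assumption, because the documents do not state it.

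| Subject | Last patch | Removal | Window end | Gap 0 | Gap 7 days | Gap 14 days |
|---|---|---|---|---|---|---|
| Completer with full taper (Protocol 7.2.1.2) | Day 110 | Day 111 | Day 141 | 30/141 = 21% | 23/141 = 16% | 16/141 = 11% |
| Lack-of-efficacy withdrawal, no taper | Day 21 | Day 22 | Day 52 | 30/52 = 58% | 23/52 = 44% | 16/52 = 31% |
| Lack-of-efficacy withdrawal on Day 22, then 4-day taper | Day 26 | Day 27 | Day 57 | 30/57 = 53% | 23/57 = 40% | 16/57 = 28% |

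The Safety Follow-Up Visit is due 30 ± 5 days after the taper, so entry before that visit falls inside the window in nearly every case.

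**3. What this does to incidence.** Let p be the true double-blind TEAE incidence in an arm. Let f be the share of its subjects who roll over and whose later events are recorded in SP1006, and q the chance of an event in the open-label part of the window. Taking these as independent,

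apparent incidence = p + (1 − p) × f × q.

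None of the three is in the documents. Purely to show the mechanism, with p = 40% for placebo:
- f = 0 gives 40%, that is, no effect.
- f = 50% and q = 40% give 0.40 + 0.60 × 0.50 × 0.40 = 52%.

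These are not estimates.

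**4. Direction.** Each arm gains (1 − p) × f × q. The difference between active and placebo shrinks if placebo gains more and widens if the active arm gains more. The documents give no f or q by arm, so the sign is not determined.

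**5. After the fix.** If the window ends the day before the first RL0007 dose, open-label days in it are 0 in every row, and apparent incidence returns to p.

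**The case against.** The strongest reply is that the rule can classify only events that are in the SP1006 data, and little may get there after rollover. Protocol 11.1.1.1 requires events during the study and in post-treatment periods that the protocol requires. A rollover subject has no Safety Follow-Up Visit, so no SP1006 collection of non-serious events is scheduled after entry. The serious-event request in Protocol 11.1.2.3 leads to a report form and the global safety database; it does not say that such events enter the clinical database behind the tables. The completed adolescent study SP1004 had no serious events at all (Protocol 5.4). This stands, and it is why the effect may be nil. It does not remove the gap. SAP 3.2.2 expressly plans to analyse events dated after the last assessment, and Protocol 11.1.3 provides for follow-up of ongoing events, usually for 30 days after treatment stops. A rule that is right only if data capture happens to exclude these events should say so.

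There is also some mitigation. All adverse events are listed, and SAP 3.2.1.1 marks relative days after last patch removal with a plus sign. Post-patch events can therefore be seen, but rollover itself is not flagged. The safety analysis is descriptive, so no test depends on the window.

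A reader might infer three stronger things that the documents do not support:
- **That the rule dilutes the safety difference between the arms.** All arms may roll over, and step 4 of the working shows that the sign depends on unknown rates.
- **That both primary safety variables are exposed.** Under SAP 10.2 an event leads to discontinuation only if the AE page records permanent withdrawal of study medication. An event that starts after the last SP1006 patch can hardly meet that.
- **That the open-label drug is certainly rotigotine.** This is a natural inference, but neither document names the RL0007 treatment.

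**Conclusion.** The point holds as a defect in a stated rule. As written, SAP 10.2 and 3.2.2 assign to the randomised arm, placebo included, any event recorded in SP1006 that starts within 30 days of last patch removal, even if it starts after the first RL0007 dose. No section censors, flags or reassigns such events.

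The exposed time is at most about 21% of the window for a completer, and 53% to 58% for a subject who leaves for lack of efficacy straight after titration. These are maximum shares of calendar days with immediate rollover, not shares of events. The number of misassigned events and the direction of any bias are unknown, and both may be nil. They depend on rollover numbers and timing by arm, on what RL0007 gives, and on whether events after rollover are entered in the SP1006 database. The change is worth making because the TEAE tables by arm are among the main results left and the correction is small.

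**What to change.** In SAP 10.2, and in the matching sentence of SAP 3.2.2, define the end of the TEAE window for rollover subjects as the earlier of (a) 30 days after last SP1006 patch removal and (b) the day before the first RL0007 dose. Apply the same end date to worsening of pre-existing events. List any later event recorded in SP1006 separately, by randomised arm and marked as after RL0007 entry, so that no safety information is lost. Where a partial date leaves the side of the boundary unclear, keep the existing SAP 4.2.2 convention of treating the event as treatment-emergent. Report the number of rollovers by arm beside the TEAE overview, so that the reader can judge the exposure.

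The cost is a short SAP amendment, which SAP section 1 allows before database lock, and one added listing. The real requirement is a date from another study. The RL0007 first-dose date or, if that is unavailable, the RL0007 entry date must be brought into the SP1006 analysis data. The documents do not say that it is already there.

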10.3 Clinical laboratory evaluations

The following laboratory parameters are measured within the study:

- Hematology parameters: Hematocrit, Hemoglobin, Platelets, Red Blood Cells, White Blood Cells, and differential count and percentile (Lymphocytes, Basophils, Eosinophils, Monocytes, Neutrophils)
- Liver Function Tests and other Chemistry parameters: Alanine Aminotransferase (ALT), Aspartate Transaminase (AST), Albumin, Alkaline Phosphatase (ALP), Bicarbonate, Blood Urea Nitrogen, Calcium, Chloride Creatinine, Ferritin, Gamma-glutamyl transferase, Glucose, Iron Binding Capacity Total, Iron Binding Capacity Unsaturated, Lactate Dehydrogenase, Potassium, Phosphorus, Serum Iron, Sodium, Total cholesterol, Total bilirubin, Total protein, Transferrin, Uric acid
- Endocrine parameters: Estradiol (females only), Follicle-stimulating Hormone (FSH), Insulin-like Growth Factor 1 (IGF-1), Luteinizing Hormone (LH), Progesterone (females)

only), Prolactin, Testosterone (males only), Thyroxine Free (T4FR), Triiodothyronine (T3), Thyroid Stimulating Hormone (TSH)

– Endocrine normal ranges are provided by the central lab and included in the dataset specifications.

- Urinalysis: Color, Appearance, Glucose, Protein, Blood, Ketones, Urine Pregnancy Test

Summary statistics of the observed values and their change from Baseline and the frequency of abnormal values based on normal ranges will be presented by visit for laboratory parameters of hematology, chemistry and endocrinology.

Laboratory data outside the reference range will be highlighted with “L” for low and “H” for high in all laboratory subject data listings where applicable. Individual subject data listings will be presented for laboratory parameters of hematology, chemistry and endocrinology. Urinalysis and pregnancy test results will only be listed.

